Study Protocol

Official Title: SOVA Ambassadors Community Setting

ClinicalTrials.gov ID (NCT number): NCT06066697

Date of document creation: 8/23/2023

Date of last modification: 9/24/2025

Scientific Background

Despite the significant mental health need in this age group, less than half receive treatment, initial treatment is delayed by 10 years. For anxiety, less than one-fifth use mental health services. Unmet treatment needs are even more concerning for lower-income youth and especially for racial/ethnic minorities who face even higher rates of depression and anxiety with fewer accessing care. These youth are disproportionately affected by adverse childhood experiences, traumatic experiences like discrimination, known predictors of poor adult functioning and contribute to disparities in mental health.

Racial/ethnic minority youth experience multiple barriers to obtaining mental health treatment. A systematic review found the most important barriers for young people overall are a lack of mental health knowledge and negative beliefs about treatment. Negative beliefs in racial/ethnic minority youth are complex, including factors such as wanting to appear tough in front of peers in African American males or not wanting to feel judged among Mexican youth. Youth also may have concerns mental health providers will lack cultural competence. Despite barriers, youth actively talk about experiences with depression and anxiety online and adolescents with unmet mental health needs more frequently use social media (SM) to seek support. While there are some concerns about SM the literature is mixed and moderated sites have been found to be helpful. A moderated SM site for adolescents with depression was highly usable and improved depression scores. Almost all (95%) adolescents have access to a smartphone; this does not vary by race or income. An online environment may be best suited to address health beliefs, as adolescents discuss their depressive symptoms online and use SM for identity exploration and social norms setting. The online environment, especially for racial/ethnic minority youth who are less likely to find help elsewhere, is a point of entry to talk about mental health and find support.

Partnership between SOVA research team and Focus on Renewal (FOR) community agency was formed as part of a CTSI sponsored Community Research Dissemination Challenge called WordOut. FOR provides summer workforce development program in the summer through Learn & Earn to the Sto Rox community where mean household income is \$25,000 and 28% of population is under 18. We administered a mental health curriculum covering various topics to a small group of 5 throughout, and large group of 25 at the end of program. We frequently offered participation in SOVA Peer Ambassador Program. Although youth expressed interest and practiced writing about mental health topics, none engaged in SOVA. FOR Learn & Earn Administrators gave feedback implementation of the program in their setting may improve if the program is introduced to them by other youth and advocates from their community, framed as a career development opportunity and not a mental health program. This informed us that prior to piloting SOVA in a community setting, we needed to take a more calculated approach to understanding what type of implementation strategy may be most effective. We utilized the process of implementation mapping with program administrators of workforce development programs, community leaders, and youth. We gained instrumental feedback from program administrators who facilitate workforce development programs and from our youth research partners. Briefly, the programs envision all yearly 1300 adolescent low-income participants would benefit from the psychoeducational content on the SOVA websites. Instead of the SOVA Peer Ambassador Program serving as a separate worksite to teach an employable skill of writing, the program administrators advised to provide the program as an adjunct activity available to any adolescent. This would also allow the SOVA content and the opportunity to enter the study to be

introduced to youth in multiple programs by our current youth junior researchers during the 6-week summer program, but be available as a longitudinal activity continuing even after the workforce program ends.

Study Objectives

Conduct a 1:1 pilot randomized controlled trial of the SOVA Peer Ambassador Program compared to attention control: brief psychoeducational independent assignments (i.e. reading SOVA articles and responding to open-ended questions without content creation and without peer interaction) (N=40) and evaluate feasibility of implementation strategy. All participants will have access to read content on the SOVA sites, but only Ambassadors will be able to log-in and invited to create content to share with others. We will examine participant adherence to intervention feasibility and acceptability of intervention, attention control, and implementation strategy. We will also assess acceptability of randomization, feasibility of recruitment, quality of training, trainer fidelity. We will generate preliminary data on outcomes, refine proposed study measurements, and assess preliminary effectiveness on resilience.

Study Design & Methods

This intervention trial will use a randomized trial design where each of the 40 participants is randomly assigned to one of two arms. Adolescents will be randomized at a 1:1 ratio (using randomized block sizes). The arms are SOVA Peer Ambassador Program and attention control: brief psychoeducational independent assignments.

1) conduct a pilot RCT comparing SOVA Peer Ambassador Program to attention control to understand feasibility and acceptability of Ambassador Program and accompanying implementation strategy. Adolescents will be randomized at a 1:1 ratio (using randomized block sizes). The primary endpoint is feasibility of the intervention. Expected Outcomes: We anticipate to learn if the SOVA Peer Ambassador intervention is feasible in a work readiness program setting for low-income adolescents consisting of mostly racial minority youth. We also anticipate to understand feasibility and acceptability of the attention control, implementation strategy, refine proposed study measurements, measure cross-over between groups, and find if there is preliminary effectiveness.

Adolescents who are interested in the study will provide their contact information to the research team and schedule a phone call or video call using Zoom if they prefer. We will also offer a link to appointment times so they can self-schedule this call. During the initial phone call adolescents will undergo screening procedures. Screening will involve inquiring about inclusion/exclusion criteria including asking the PHQ-8 measure and the GAD-7 measure. If inclusion/exclusion criteria is met, the research assistant will proceed to obtaining assent from the adolescent participants. Consent will be obtained from participants between 18 and 21 years. Once written assent/consent is obtained electronically and documented, the adolescent will be sent a baseline survey by text message via REDCap. Preferably, the adolescent will complete the baseline while the research assistant waits. If the adolescent prefers to complete it later, they will schedule a

follow-up call with the research assistant. Enrollment tracking will be conducted by using a RedCAP database which was successfully used by our research team in prior pilot efficacy studies of SOVA. We will use this database to keep track of all episodes of screening, consent, participant payment, and data point completion. Once they complete the baseline survey, then the research assistant will individually randomize them 1:1 (using REDCap) to either the SOVA ambassador arm or the Attention control arm.

If randomized to the SOVA Ambassador arm, the research assistant will provide an onboarding tutorial of the SOVA website contribution expectations. First, users will be asked to provide a username and email they would like to use for the website. The research assistant (RA) will create a login for them for the site. Participants will be asked to not post identifying information on the site and if they do, the site moderator will remove it. By creating a username, they will receive weekly email notifications about new posts. Participants will be notified that the researchers will use the website to track log-in frequency, log-in duration frequency, and website use. Also, any online text will be downloaded and qualitatively analyzed as well - unless the text contains identifying information - in that situation, this content will be permanently deleted. The Ambassador phone call will include information about compensation, blogging expectations, and procedures. There will be disclaimer about safety tips, and reminding participants this website is not an alternative to therapy or other treatment. The RA will share expectations of participating in the SOVA intervention which is to contribute content to the SOVA website at least once a month either by (1) writing a blog article. They can choose what they would like to write about and they will work with a SOVA team member who will edit and provide thoughtful feedback. They will be encouraged to • share personal experiences • share stories • give advice to other members (2) sending information (de-identified photo or video or music) to post. If they choose this option they will be encouraged to submit their own photo, video, or music to the website or they will be encouraged to write a response to a photo, video, or music piece. (3) being interviewed by the RA and then the RA "ghostwriting" an article about the interview which they pre-approve prior to it being posted. • If they choose this option they will get a series of topics and questions to choose from. e.g. people often can disagree – family, friends, partners, co-workers, or random people, offline or online, can you talk about how disagreements in your or others' lives can affect your stress or mental health? If randomized to the Attention Control arm, the research assistant will provide an onboarding tutorial of the expected contributions. This will include going to redcap form where they will receive a link to a SOVA article to read and a question for them to answer about what they read that will be accessible only to the study team. They will be asked to do this a couple times a month and will be reminded about their participation. The articles will be about mental health found on the website sova.pitt.edu. The question asked of the participants in this study arm will be open ended. An example of this will be: The article talked about different types of therapy. What types of therapy do you have experience with? If you do not have experience with the types of therapy which type of therapy do you think is most interesting? Then describe why or why not. Both arm participants will fill out online surveys via REDCap at baseline 6 weeks and 12 weeks. These surveys will take about 30 minutes to complete.

Eligibility Criteria

List the inclusion criteria:

Adolescents Ages 14 to 21 Can read and understand English Has completed 6th grade Scores at least 5 or greater on the PHQ-8 (depression) and/or 5 or greater on GAD-7 (anxiety) consistent with at least mild symptoms

List the exclusion criteria:

Adolescent no access to internet Has an intellectual or physical ability which prohibits reading text on the internet (can participate if able to use with assistance, e.g. can use text to speech) No active email account (can participate if plans to create one)

Statistical Considerations

Methods for sample size: Feasibility of the intervention will be established if an average of 2.3 articles are written per individual over the 12 weeks. This is because anticipating a SD of 0.5, that would give us a confidence interval width of 0.59 with a sample of $N = 20$. If results are very skewed, we will log transform any outliers. We have designated this sample size due to budgetary and programmatic constraints. Programs typically have 20 adolescents enrolled, so as we anticipate involving 2 programs, 40 total could be enrolled (20 in the intervention, 20 in the control).

Feasibility of the intervention will be established if an average of 2.3 articles are written per individual over the 12 weeks. This is because anticipating a SD of 0.5, that would give us a confidence interval width of 0.59 with a sample of $N = 20$. If results are very skewed, we will log transform any outliers. We have designated this sample size due to budgetary and programmatic constraints.

Data analysis: Our main goal is to understand feasibility of the pilot trial. Engagement with the SOVA Peer Ambassador intervention will be the main outcome and will be determined by the average number of articles written per participant at 12 weeks. We will use summary statistics (frequencies and percentages for categorical variables; means (standard deviations); and medians (ranges) for continuous measures) to describe measures. We will follow all recommendations from the pilot CONSORT statement. We will record number, percentage survey items missing and will summarize. We will capture proximal and main outcomes listed in Table 1 by study arm and assess change (from baseline to 6-week, and baseline to 12-week) using a linear mixed model for continuous outcomes. We will use a linear mixed model to estimate initial associations between treatment arm and resilience outcomes. The statistician conducting analyses will be blinded to randomized arm. Sample size: Feasibility of the intervention will be established if an average of 2.3 articles are written per individual over the 12 weeks. This is because anticipating a SD of 0.5, that would give us a confidence interval width of 0.59 with a sample of $N = 20$. If results are very skewed, we will log transform any outliers. We have designated this sample size due to budgetary and programmatic constraints. Expected Outcomes: We anticipate to learn if the SOVA Peer Ambassador intervention is feasible in a work readiness program setting for low-income adolescents consisting of mostly racial minority youth. We also anticipate to understand feasibility and acceptability of the attention control, implementation strategy, refine proposed

study measurements, measure cross-over between groups, and find if there is preliminary effectiveness.

Engagement with the SOVA Peer Ambassador intervention will be the main outcome and will be determined by the average number of articles written per participant at 12 weeks. We will use summary statistics (frequencies and percentages for categorical variables; means (standard deviations); and medians (ranges) for continuous measures) to describe measures. We will follow all recommendations from the pilot CONSORT statement. We will record number, percentage survey items missing and will summarize. We will capture proximal and main outcomes listed in Table 1 by study arm and assess change (from baseline to 6-week, and baseline to 12-week) using a linear mixed model for continuous outcomes. We will use a linear mixed model to estimate initial associations between treatment arm and resilience outcomes. The statistician conducting analyses will be blinded to randomized arm.

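### Log-transforming only the outlying article counts would mix two scales in the average judged against 2.3 articles, and can turn a met feasibility criterion into a missed one

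*Combined protocol and SAP*

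**What the plan says.** Study Design & Methods names the endpoint: "The primary endpoint is feasibility of the intervention". Statistical Considerations gives it a threshold: "Feasibility of the intervention will be established if an average of 2.3 articles are written per individual over the 12 weeks". The precision statement follows ("anticipating a SD of 0.5, that would give us a confidence interval width of 0.59 with a sample of" 20), and then the rule at issue: "If results are very skewed, we will log transform any outliers".

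These sentences appear three times in the same order: in the paragraph on methods for sample size, in the paragraph after it, and in the sample-size part of the Data analysis paragraph. No other outcome is named in any of these blocks.

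The Data analysis paragraph defines the main outcome as engagement, which "will be determined by the average number of articles written per participant at 12 weeks". The closing paragraph of the document repeats that analysis text without any log step. Both also plan means with SDs and medians with ranges.

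**The concern.** The rule transforms the outliers, not the variable. Some participants would be scored in articles and others in log-articles, and the two would be averaged. That average is not the number of articles per participant that the plan defines as its main outcome, and 2.3 articles is not a threshold for it.

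Rank order can also break. With natural logs, a flagged count from 4 to 7 scores below an unflagged 2 (ln 7 = 1.946), and one from 4 to 20 scores below an unflagged 3 (ln 20 = 2.996). Three is roughly what the expectation in Study Design & Methods implies, which is to "contribute content to the SOVA website at least once a month". A very active contributor could therefore count for less than one who just meets expectations. A zero has no logarithm.

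The plan does not say what makes results very skewed, what makes a count an outlier, which log base applies, or whether altered values feed the criterion. If they do, the primary verdict could rest on choices made after the counts are seen.

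**Working it through.** **Inputs from the documents.** Threshold 2.3 articles; anticipated SD 0.5; stated interval width 0.59; 20 participants in the SOVA arm ("40 total could be enrolled (20 in the intervention, 20 in the control").

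**Assumptions.** The documents give no article counts, so the data sets below are invented. Met means a mean of at least 2.3. An outlier lies more than 1.5 × IQR outside the quartiles. Natural log is used unless another base is named.

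**The plan's own figure.** A plain 95% t interval has width 2 × 2.093 × 0.5/√20 = 0.468, not 0.59. With a 95% assurance factor, √(30.144/19) = 1.260, the width is 0.468 × 1.260 = 0.59. The figure therefore reproduces, but only with an assurance level that the plan does not state. That is a separate reporting gap, and nothing below depends on it.

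**Set 1: thirteen 2s, six 3s, one 5.**
- Raw mean (26 + 18 + 5)/20 = 2.45, SD 0.759: met.
- Quartiles are 2 and 3, so the fences are 0.5 and 4.5. The 5 is the only outlier, and also lies (5 − 2.45)/0.759 = 3.36 SD above the mean.

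| Scale used for the 5 | Mean | Verdict |
|---|---|---|
| Raw | 49/20 = 2.45 | met |
| ln | (44 + 1.609)/20 = 2.28 | not met |
| log10 | (44 + 0.699)/20 = 2.23 | not met |
| log2 | (44 + 2.322)/20 = 2.32 | met |
| ln(x+1) | (44 + 1.792)/20 = 2.29 | not met |

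**Set 2: fourteen 2s, five 3s, one 8.** Raw mean 51/20 = 2.55, met. With the 8 logged, (43 + 2.079)/20 = 2.25, not met.

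**A set that does not change: ten 2s, nine 3s, one 10.** Raw mean 57/20 = 2.85; with the 10 logged, (47 + 2.303)/20 = 2.47. Both met.

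**General size.** Logging one count k among 20 lowers the mean by (k − ln k)/20. The verdict reverses only if the raw mean is at least 2.30 and below 2.30 plus that shift.

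| k | Shift | Raw means that reverse |
|---|---|---|
| 5 | (5 − 1.609)/20 = 0.170 | 2.30 to 2.470 |
| 8 | (8 − 2.079)/20 = 0.296 | 2.30 to 2.596 |
| 10 | (10 − 2.303)/20 = 0.385 | 2.30 to 2.685 |

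Because ln k < k for every positive k, the shift for counts that can be logged is always downward.

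**Zero case: one 0, twelve 2s, seven 3s.** Raw mean 45/20 = 2.25, not met. The zero is the only outlier (below the fence of 0.5, and 2.25/0.716 = 3.14 SD below the mean) and cannot be logged. If it were then treated as missing, which the plan does not say, the mean becomes 45/19 = 2.37, met.

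**How often, under assumed distributions.** In simulations of 20 counts with high outliers logged:
- Normal counts rounded to integers (mean 2.5, SD 0.5 before rounding) went from met to not met in about 0.2% of trials.
- Poisson counts with mean 2.5 did so in about 15%.
- Strongly overdispersed counts (negative binomial, mean 2.5, variance 2.5 + 2.5² = 8.75) did so in about 27%.
- If the rule applies only when sample skewness exceeds 1, the last two figures become roughly 5% and 26%. Poisson rates fall as the mean rises further above 2.3.

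**The case against.** The strongest reply is that no sentence says logged values decide the criterion. The threshold and the main outcome are both worded in articles, and the log sentence follows the interval-width statement, so it may be meant only to protect the SD or the interval. On that reading the verdict stays on raw counts. The reading is possible but the plan does not state it, and an interval computed from part-logged counts would not describe the mean being judged.

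A second reply is that the sponsor meant to log the whole variable when it is skewed. The text says outliers. Logging everything would not repair the criterion either: a back-transformed geometric mean is a different quantity from the stated average (2.36 against 2.45 in Set 1), and zeros would still fail.

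Third, under the planned SD of 0.5 a reversal is rare. That stands, but the rule is written for very skewed data, where an SD of 0.5 is least credible. The reversing sets above have SDs of 0.76 and 1.36.

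Fourth, the zero case needs left-skewed data and an unstated decision to drop the value. This is fair. It is secondary, and it runs in the opposite direction to the main risk.

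Finally, this is a pilot with medians and ranges already planned, so a reader could see a single heavy contributor. That softens the harm but does not settle which mean is compared with 2.3.

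**Conclusion.** The concern holds. Applied as written, the rule gives a mean that is neither in articles nor the main outcome the plan defines, so it cannot be judged against 2.3. This is a stated procedure that can give the wrong primary result, not merely a missing detail.

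The size is limited. A single natural-logged count of 5 to 10 moves the mean by 0.17 to 0.38, so the verdict is at risk only when the raw mean is at or moderately above 2.3. The main risk is declaring a feasible programme not feasible; Set 1 shows that the choice of log base alone can decide it.

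The conclusion that the verdict can change rests on two conditions that the plan leaves open: that the skewness trigger is met, and that the altered values feed the criterion. The likelihood of the first is unknown because the documents give no article-count data. That the rule is unsuitable for this criterion depends on neither condition.

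**What to change.** Delete the log-transformation sentence at all three places. Add one sentence: the 2.3 criterion is judged on the mean of untransformed article counts for all participants randomised to SOVA, with zeros included. Naming the zeros ensures that a participant who writes nothing is not lost from the average.

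Keep the median and range already planned beside the mean. Two additions are optional. If heavy contributors are a worry, pre-specify one sensitivity analysis, for example counts capped at a stated value, that does not replace the primary result. Any interval reported can come from a bootstrap or a count model; it would not alter the verdict, because the criterion is an average.

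The cost is one sentence removed in three places and one added, with no new data. The change should be made before the article counts are analysed.

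### Does deriving N = 40 from two full program rosters of 20 leave the trial without a workable sample size?

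*Combined protocol and SAP*

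**What the plan says.** Statistical Considerations, under the sample size methods, gives the reasoning for the total: "Programs typically have 20 adolescents enrolled, so as we anticipate involving 2 programs, 40 total could be enrolled", with 20 in each arm. The same section attributes the sample size to budgetary and programmatic constraints. It also says that 20 participants with an anticipated SD of 0.5 give a confidence interval width of 0.59; the confidence level and the method are not stated.

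Study Design & Methods sets out the steps before randomisation: the youth expresses interest, takes a screening call, gives assent or consent, and completes the baseline survey. Eligibility Criteria require a score of 5 or more on the PHQ-8, the GAD-7 or both. No rate is given for any step.

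Three other places bear on the point:

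- Scientific Background reports an earlier community effort delivered "to a small group of 5 throughout, and large group of 25 at the end of program", with this outcome: "Although youth expressed interest and practiced writing about mental health topics, none engaged in SOVA". It then describes a revised approach in which the study is "introduced to youth in multiple programs by our current youth junior researchers during the 6-week summer program", and notes that "the programs envision all yearly 1300 adolescent low-income participants would benefit" from the website content.
- Study Objectives lists recruitment among the things to be evaluated: "We will also assess acceptability of randomization, feasibility of recruitment, quality of training, trainer fidelity".
- On the REDCap database, Study Design & Methods says: "We will use this database to keep track of all episodes of screening, consent, participant payment, and data point completion".

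**The concern.** The roster of a program and the number randomised from it are different quantities, and the sample size sentence moves from one to the other without a step between. Each stage before randomisation can lose people, and a symptom threshold is there to exclude some. A yield of 100% from two programs is therefore not a realistic expectation, and the one uptake observation in the documents, in which nobody engaged, lends it no support.

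Two things would be at stake. The Ambassador arm could finish with fewer than 20, so that the mean number of articles is estimated less precisely than stated. And because the study is introduced during a six-week summer program, there may be little time to add programs once a shortfall shows. A further worry is that the listed tracking begins at screening. Youth who hear about the study and do not come forward would not be counted, although recruitment feasibility is an objective.

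**Working it through.** **Inputs.** Roster 20 per program, two programs, 1:1 allocation, SD 0.5, width 0.59 at n = 20 (all from Statistical Considerations). The yield y, meaning the share of a roster that is randomised, is not in the documents. Every value of y below is an assumption, shown for range only.

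**1. Reproduce the total.** N = programs × roster × y = 2 × 20 × y. At y = 100% this is 40, the plan's figure. Any lower yield gives fewer.

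**2. What lower yields would give from two programs.**

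| Assumed y | N = 40y | Per arm |
|---|---|---|
| 90% | 36 | 18 |
| 75% | 30 | 15 |
| 50% | 20 | 10 |
| 25% | 10 | 5 |

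If youths are treated as independent, the chance that all 40 are randomised is 0.95^40 = 13% at a 95% yield and 0.90^40 = 1.5% at 90%. So 40 from exactly two programs is a ceiling and is unlikely to be met in full.

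**3. Reproduce the width before using it.** At SD 0.5 and n = 20:

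- 95% normal: 2 × 1.960 × 0.5/√20 = 0.438
- 95% t: 2 × 2.093 × 0.5/√20 = 0.468
- 99% normal: 0.576
- 99% t: 0.640
- 95% t with 95% assurance on the sample SD: 0.468 × √(30.144/19) = 0.589

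Only the last rounds to 0.59. The plan does not name this basis, so the match is an inference.

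**4. What a shortfall does to the width.**

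| Ambassadors | Plain 95% t | 95% t with 95% assurance |
|---|---|---|
| 20 | 0.468 | 0.589 |
| 19 | 0.482 | 0.610 |
| 14 | 0.577 | 0.757 |
| 10 | 0.715 | 0.981 |

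It is tempting to solve for the smallest n that keeps 0.59 with a plain 95% t interval. That gives 14 Ambassadors (0.577; 13 gives 0.604), or 28/40 = 70% of two rosters. But the plain t width at n = 20 is 0.468, so 0.59 was not obtained that way. On the basis that matches, 0.59 needs all 20. Writing a 70% requirement into the plan would tie one width to both 14 and 20 participants and create an inconsistency that is not there now.

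**5. Does anything in the analysis depend on reaching 40?** The primary result is the mean number of articles per Ambassador over 12 weeks, judged against 2.3. That mean and its interval can be computed at any n of at least 2. The mixed models for resilience and the other outcomes are described as preliminary, and no power claim is attached to them.

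**The case for a change.** The strongest case for a change is that it is cheap and the timing matters. A sentence or two could call 40 a maximum and give the number of programs to be approached. One extra count per program, the number of youth introduced, would let the pilot report yield from first contact, which a larger trial would want to know and which is hard to rebuild afterwards. A budget limit explains a cap of 40; it does not explain expecting to reach the cap from two rosters. On the matching basis for 0.59 there is no slack either: 19 Ambassadors already give 0.61.

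Much of this is true, and some of it stands. The plan makes no allowance for loss, and a count of youth introduced would be useful. But the request to call 40 a maximum largely restates what the sentence conveys, since it speaks of what is typical, what is anticipated and what could happen. The number of programs anticipated is given, and Scientific Background speaks of introducing the study in several programs, so the text does not forbid going beyond two. The missing denominator is approximated by the roster size of 20 that the plan supplies, and the database covers screening onward. The earlier uptake of nobody came from a different, since-revised approach without trial consent, and the text does not say whether the 5 were among the 25. It does not forecast yield here.

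**Conclusion.** No change is needed. The arithmetic behind the concern holds: with two programs and rosters of 20, N = 40 requires a 100% yield, and fewer than 40 is the likelier outcome. What follows is a less precise pilot. If half of each roster were randomised, the Ambassador arm would be 10 and the width would go from 0.59 to 0.98 on the basis that reproduces the plan's figure, or from 0.47 to 0.72 as a plain 95% t interval. The analyses would stay valid, the 2.3-article criterion would be applied in the same way, and a low yield would itself inform the stated recruitment objective.

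This is missing planning detail that the study team can fill in the ordinary course, by reporting the number reached against the rosters of the programs involved. The conclusion rests on three things: reading the sample size sentence as a statement of capacity, which its hedged wording supports; accepting the plan's statement that N was set by constraints; and the absence of any documented yield, so that no particular shortfall can be shown. The reading of 0.59 as a t interval with assurance is an inference. It counts against adding a required-yield figure, but the verdict does not otherwise depend on it.

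### The resilience mixed model names no between-arm contrast and no baseline adjustment; an adjusted contrast would add modest precision at almost no cost

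*Combined protocol and SAP*

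**What the plan says.** All references are to the combined protocol and SAP.

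- **Analysis.** The Data analysis text under Statistical Considerations, which appears twice with the same wording on this point, contains two relevant sentences. The first will summarise outcomes by arm and "assess change (from baseline to 6-week, and baseline to 12-week) using a linear mixed model for continuous outcomes". The second reads "We will use a linear mixed model to estimate initial associations between treatment arm and resilience outcomes". Neither mentions a baseline covariate, a common baseline mean, an arm-by-visit term, or the visit at which arms are compared.
- **Data.** Study Design & Methods has the baseline survey completed before the research assistant randomises the participant. It also states "Both arm participants will fill out online surveys via REDCap at baseline 6 weeks and 12 weeks".
- **Role of the outcome.** Study Objectives includes the aim to "assess preliminary effectiveness on resilience", while Study Design & Methods states "The primary endpoint is feasibility of the intervention".
- **Size.** Statistical Considerations expects 40 participants, 20 per arm, a number set by budget and programme size.

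**The concern.** Specifying a linear mixed model does not by itself adjust the arm comparison for baseline. If baseline, week 6 and week 12 are all outcomes and each arm has its own baseline mean, then with complete data the arm-by-visit contrast is simply the difference between arms in mean change score. If baseline is left out, the contrast is the plain difference at follow-up. Both are unbiased under randomisation. A contrast that uses the baseline score as a pre-randomisation predictor is also unbiased, and on average more precise than either at the correlations considered below.

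Chance baseline imbalance is the mechanism of the loss, not a separate harm: the change score over-corrects for it and the plain follow-up difference does not correct for it at all.

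Two things are at stake, both small. The interval for resilience is wider than it needs to be in a trial that cannot easily enlarge its sample. And because no contrast is named, which of several valid estimates will be reported is not fixed in advance.

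**Working it through.** **Inputs.** From the documents: 20 per arm, 1:1 allocation, baseline before randomisation, follow-up at 6 and 12 weeks. Not in the documents, so assumed: the correlation r between baseline and follow-up resilience (0.3 to 0.9), equal SDs at both times (set to 1), and the number analysed (20 per arm, with 16 as a sensitivity case). The plan gives no precision figure for resilience to reproduce; its only calculated figure concerns articles written.

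**Formulas**, for the between-arm difference at one follow-up visit with n per arm:

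- Change from baseline: (2/n) × 2(1 − r)
- Follow-up only: 2/n
- Baseline-adjusted: (2/n) × (1 − r²) × [1 + 1/(2n − 4)]

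The last factor is the average cost of estimating the baseline slope: 1 + 1/36 = 1.0278 at n = 20 and 1 + 1/28 = 1.0357 at n = 16. Half-widths use t on 2n − 2 degrees of freedom, or 2n − 3 when adjusted.

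**Worked case, r = 0.5, n = 20** (2/n = 0.1). Change: 0.1 × 1.0 = 0.100. Adjusted: 0.1 × 0.75 × 1.0278 = 0.0771. Ratio: 0.100/0.0771 = 1.297. Half-widths: 2.024 × √0.100 = 0.640 and 2.026 × √0.0771 = 0.563 SD.

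**Range of r, n = 20**

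| r | Variance ratio, change / adjusted | Variance ratio, follow-up only / adjusted | Half-width, change (SD) | Half-width, adjusted (SD) |
|---|---|---|---|---|
| 0.3 | 1.497 | 1.069 | 0.757 | 0.620 |
| 0.5 | 1.297 | 1.297 | 0.640 | 0.563 |
| 0.7 | 1.145 | 1.908 | 0.496 | 0.464 |
| 0.8 | 1.081 | 2.703 | 0.405 | 0.390 |
| 0.9 | 1.024 | 5.121 | 0.286 | 0.283 |

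The follow-up-only half-width is 0.640 SD at every r. Against the change contrast, adjustment shortens the interval by about 18%, 12%, 6%, 4% and 1%.

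**Sensitivity, n = 16.** Change/adjusted variance ratios are 1.485, 1.287, 1.136, 1.073 and 1.016, so dropout to 32 analysed hardly alters the comparison.

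**Simulation** (20,000 trials per r, n = 20, true difference 0.5 SD, one follow-up visit, baseline as covariate). All three estimators averaged 0.496 to 0.504, confirming no bias. The change/adjusted variance ratios were 1.49, 1.32, 1.15, 1.07 and 1.03, in line with the formula. The adjusted interval was narrower than the change interval in 99.1%, 96.0%, 84.4%, 72.7% and 52.2% of trials (n = 16: 97.8%, 92.6%, 78.6%, 65.1% and 46.8%).

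**The case against.** The strongest reply is that nothing here is wrong. Baseline is already used, through change from baseline; the unadjusted estimates are unbiased; and a short pilot plan that says only linear mixed model leaves room for a baseline term. That is all true, and it is why this is a suggestion and not a correction.

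The outcome is also peripheral and the sample was not sized for it. For a true difference of 0.5 SD at r = 0.5, approximate power rises only from 35% to 44%, so the reading of the result would seldom change. That stands too.

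The size of the gain depends on a correlation that the documents do not give. Taking whichever unadjusted reading loses less at each r, the excess variance is 7%, 30%, 14%, 8% and 2%. The large follow-up-only losses at high r belong to the less natural reading and should carry little weight. Nor is the gain assured in each trial: at r = 0.9 with 16 per arm the adjusted interval was the narrower one less than half the time, though the average penalty is negligible.

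Finally, a constrained-baseline mixed model fitted by maximum likelihood with normal quantiles under-covers in samples this small: about 93% at 20 per arm and 92% at 16 for a nominal 95% interval. The covariate model with t quantiles held 95%. This is a small-sample matter that affects the planned mixed model as well. It does not count against adjustment, but the fix should address it.

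**Conclusion.** The point holds, as a low-severity improvement. The plan commits to a resilience comparison without naming the contrast, the visit or any baseline adjustment, while already collecting what adjustment needs. Under equal SDs and 20 analysed per arm, the gain over the change contrast is worthwhile at r of 0.3 to 0.5, small at 0.7 or higher and negligible at 0.9. Since r is unknown in advance, the adjusted contrast is the safer choice: change scores do poorly when r is low, plain follow-up differences do poorly when it is high, and adjustment was on average at least as precise as both over the range shown. The resilience estimate stays imprecise whichever contrast is used.

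**What to change.** In both places where the Data analysis text appears, define the resilience effect as the between-arm difference at 6 weeks and at 12 weeks, each with a 95% CI, from a mixed model with visit-specific arm effects. Use one of two forms:

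- baseline score as a covariate, with only the two follow-up visits as outcomes; or
- all three visits as outcomes, with baseline means constrained equal across arms.

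State that intervals use a small-sample method (t-based degrees of freedom, not normal quantiles). The planned summaries of change from baseline can stay.

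The cost is one or two sentences in the plan and one degree of freedom for the baseline slope. No further data collection is needed, and the feasibility analysis does not change.
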